## 6 Safety monitoring

### 6.1 Adverse events

An adverse event (AE) is any untoward medical occurrence (i.e., any unfavourable and unintended sign [including abnormal laboratory findings], symptom or disease) in a subject or clinical investigation subject *after providing written informed consent* for participation in the study. Therefore, an AE may or may not be temporally or causally associated with the use of a medicinal (investigational) product.

The occurrence of adverse events should be sought by non-directive questioning of the patient at each visit during the study. Adverse events also may be detected when they are volunteered by the patient during or between visits or through physical examination, laboratory test, or other assessments.

Abnormal laboratory values or test results constitute adverse events only if they fulfil at least one of the following criteria:

- they induce clinical signs or symptoms,
- they are considered clinically significant,
- they require therapy.

Clinically significant abnormal laboratory values or test results should be identified through a review of values outside of normal ranges/clinically notable ranges, significant changes from baseline or the previous visit, or values which are considered to be non-typical in patient with underlying disease. Investigators have the responsibility for managing the safety of individual patient and identifying adverse events. Alert ranges for labs and other test abnormalities are included in Appendix 1.

Adverse events should be recorded in the Adverse Events CRF under the signs, symptoms or diagnosis associated with them accompanied by the following information.

- the severity grade
  - mild: usually transient in nature and generally not interfering with normal activities
  - moderate: sufficiently discomforting to interfere with normal activities
  - severe: prevents normal activities
- its relationship to the investigational treatment (no/yes), or

- its duration (start and end dates) or if the event is ongoing an outcome of not recovered/not resolved should be reported.
- whether it constitutes a serious adverse event (SAE)
- action taken regarding investigational treatment
- whether other medication or therapies have been taken (concomitant medication/non-drug therapy)
- its outcome (not recovered/not resolved; recovered/resolved; recovering/resolving, recovered/resolved with sequelae; fatal; or unknown)

## 6.2 Serious adverse events

### 6.2.1 Definition of SAE

An SAE is any adverse event (appearance of (or worsening of any pre-existing) undesirable sign(s), symptom(s) or medical condition(s) which meets any one of the following criteria

- is fatal or life-threatening
- results in persistent or significant disability/incapacity
- constitutes a congenital anomaly/birth defect
- requires inpatient hospitalization or prolongation of existing hospitalization, unless hospitalization is for :
  - routine treatment or monitoring of the studied indication, not associated with any deterioration in condition
  - elective or pre-planned treatment for a pre-existing condition that is unrelated to the indication under study and has not worsened since signing the informed consent
  - treatment on an emergency outpatient basis for an event not fulfilling any of the definitions of a SAE given above and not resulting in hospital admission
  - social reasons and respite care in the absence of any deterioration in the patient's general condition
- is medically significant, i.e. defined as an event that jeopardizes the patient or may require medical or surgical intervention to prevent one of the outcomes listed above.

All malignant neoplasms will be assessed as serious under “medically significant” if other seriousness criteria are not met.

**Unlike routine safety assessments, SAEs are monitored continuously and have special reporting requirements; see Section 7.2.**

All adverse events should be treated appropriately. Treatment may include one or more of the following: no action taken (i.e. further observation only); [study/investigational] (*select*) treatment dosage adjusted/temporarily interrupted; study drug(s) permanently discontinued; concomitant medication given; non-drug therapy given. The action taken to treat the adverse event should be recorded on the Adverse Event CRF.

Once an adverse event is detected, it should be followed until its resolution or until it is judged to be permanent, and assessment should be made at each visit (or more frequently, if

necessary) of any changes in severity, the suspected relationship to the investigational treatment, the interventions required to treat it, and the outcome.

Information about common side effects already known about the investigational drug can be found in the Investigator Brochure (IB) or will be communicated between IB updates in the form of Investigator Notifications. This information will be included in the patient informed consent and should be discussed with the patient during the study as needed.

The investigator should also instruct each patient to report any new adverse event (beyond the protocol observation period) that the patient, or the patient's personal physician, believes might reasonably be related to study treatment. This information should be recorded in the investigator's source documents, however, if the AE meets the criteria of an SAE, it must be reported to Novartis.

### **6.2.2 SAE reporting**

To ensure patient safety, every SAE, regardless of causality, occurring after the patient has provided informed consent and until 30 days *following the last administration of study treatment* must be reported to Novartis within 24 hours of learning of its occurrence. Any SAEs experienced after the 30 days period should only be reported to Novartis if the investigator suspects a causal relationship to study treatment.

Recurrent episodes, complications, or progression of the initial SAE must be reported as follow-up to the original episode, regardless of when the event occurs. This report must be submitted within 24 hours of the investigator receiving the follow-up information. An SAE that is considered completely unrelated to a previously reported one should be reported separately as a new event.

Information about all SAEs (*either initial or follow up information*) is collected and recorded on the paper Serious Adverse Event Report Form. The investigator must assess the relationship to *each specific component of study treatment (if study treatment consists of several drugs)* complete the SAE Report Form in English, and send the completed, signed form by fax within 24 hours after awareness of the SAE to the local Novartis Drug Safety and Epidemiology Department. The telephone and fax number of the contact persons in the local department of Drug Safety and Epidemiology, specific to the site, are listed in the investigator folder provided to each site. The original copy of the SAE Report Form and the fax confirmation sheet must be kept with the case report form documentation at the study site. Follow-up information should be provided using a new paper SAE Report Form stating that this is a follow-up to a previously reported SAE

Follow-up information provided should describe whether the event has resolved or continues, if and how it was treated, whether the treatment code was broken or not and whether the patient continued or withdrew from study participation. Each re-occurrence, complication, or progression of the original event should be reported as a follow-up to that event regardless of when it occurs.

If the SAE is not previously documented in the Investigator's Brochure or Package Insert (new occurrence) and is thought to be related to the investigational treatment a Drug Safety and Epidemiology Department associate may urgently require further information from the investigator for Health Authority reporting. Novartis may need to issue an Investigator Notification (IN) to inform all investigators involved in any study with the same

investigational treatment that this SAE has been reported. Suspected Unexpected Serious Adverse Reactions (SUSARs) will be collected and reported to the competent authorities and relevant ethics committees in accordance with Directive 2001/20/EC or as per national regulatory requirements in participating countries.

Local Novartis Turkey Drug Safety Department will report all suspected unexpected serious adverse reactions (SUSARs) to Ministry of Health as per The Regulation on Clinical Trials and Guidance on the collection, verification and submission of Adverse Event/Reaction Reports Occurring During Clinical Trials of Medicinal Products and Biological Products

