### **5.5.5 Permitted dose adjustments and interruptions of study treatment**

The first dose will be started as 300 mg IV.. At the end of the first month, an analysis will be conducted to assess the complete, partial, and non-responders to canakinumab treatment by physician.

Partial responders will be able take the 2nd canakinumab dose as 300 mg IV infusion at the first month then will continue the canakinumab treatment with 150 mg IV infusions at monthly intervals for 4 times. The complete responders will continue the canakinumab treatment with 150 mg IV infusions at monthly intervals for 5 times. Non-responder or deteriorating patients will be dropped from the study at the first month evaluations.

At the end of the 6th month the administration route can be switched to subcutaneous injection.

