### **5.5.8 Prohibited Treatment**

The following treatments are NOT allowed prior to baseline (time intervals prior to baseline are detailed below) AND during the entire study:

- Etanercept in the 4 weeks prior to the baseline visit (Day 0) and thereafter
- Riloncept in the 3 weeks prior to the baseline visit (Day 0) and thereafter
- Adalimumab in the 8 weeks prior to the baseline visit (Day 0) and thereafter
- Infliximab in the 12 weeks prior to the baseline visit (Day 0) and thereafter
- Rituximab in the 26 weeks prior to the baseline visit (Day 0) and thereafter
- Any other investigational biologics in the 8 weeks prior to the baseline visit (Day 0) and thereafter (with the exception of anakinra therapy –see below)
- Kineret (anakinra therapy) 3 days prior to the baseline visit (Day 0) and thereafter
- Leflunomide in the 4 weeks prior to the baseline visit (Day 0) and thereafter. After the completion of leflunomide treatment a cholestiramine in dose 8 g 3 times per day for 14 days is recommended.
- Thalidomide in the 2 weeks prior to the baseline visit (Day 0) and thereafter
- Cyclosporine in the 2 weeks prior to the baseline visit (Day 0) and thereafter
- i.v. immunoglobulin (i.v. Ig) in the 8 weeks prior to the baseline visit (Day 0) and thereafter
- 6-Mercaptopurine, cyclophosphamide, or chlorambucil in the 12 weeks prior to the baseline visit (Day 0) and thereafter
- Dapsone, in the 3 weeks prior to the baseline visit (Day 0) and thereafter
- Corticosteroids  $\geq 20\text{mg/day}$  or  $>0.4 \text{ mg/kg}$ , whichever applies, in the 1 week prior to the baseline visit (Day 0) and thereafter
- Live vaccinations within 3 months prior to the start of the trial, during the trial, and up to 3 months following the last dose.
- Use of other investigational non-biological drugs at the time of enrollment, within 30 days or 5 half-lives of enrolment, whichever is longer.
  - Intravenous methyl prednisolone pulse treatment within the last month

The investigator should instruct the patient to notify the study site about any new medications he/she takes after the start of the study drug. All medications and significant non-drug therapies (including physical therapy and blood transfusions) administered after the patient starts treatment with study drug must be listed on the Concomitant medications/Significant non-drug therapies after start of study drug.

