## 5.7 Patient demographics/other baseline characteristics

Patient demographic and baseline characteristic data to be collected on all patients include: date of birth, age, sex, ethnicity, patient referral source, relevant medical history/current medical condition present before signing informed consent. Where possible, diagnoses will be recorded, not symptoms.

Subjects should be seen for all post-baseline visits on the designated day with the allowance of a  $\pm 7$  day window for all visits. Subjects who discontinue study drug before completing the study, and those who prematurely withdraw from the study for any reason, should be scheduled for a visit 8 weeks ( $\pm 1$  week) after their last infusion /injection, at which time all of the assessments listed for the final visit will be performed.

Subjects who discontinue study drug also should return for a last assessment. If they refuse to return for this or are unable to do so, every effort should be made to contact them or a knowledgeable informant by telephone to determine the reason for discontinuation. At a minimum, they will be contacted for safety evaluations during the 30 days following the last dose of study drug, including final contact at the 30-day point. Documentation of attempts to contact the patient should be recorded in the patient record.

Information that will be collected on subjects who are screened but not enrolled includes patient demographics (age, gender, and ethnicity) and primary reason for not continuing.

If a patient discontinues before entering Visit 1, only the demographic information and Screening Log entry with the primary reason for discontinuation should be completed on the CRF. It is not necessary to complete all the required evaluations at the time of discontinuation unless medically indicated.

At screening visit information on age, sex, will be collected. Relevant medical history/current medical conditions, family medical history, will be recorded on the respective CRF page. The following should be recorded on the respective CRF page.

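### All-cause SAE reporting ends 30 days after the last dose, before the plan's own 8-week assessment of early stoppers, and completers have no contact specified after Day 360

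*Combined protocol and SAP*

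**What the plan says.** **SAE reporting (section 6.2.2).** From consent until 30 days after the last administration, every SAE must go to the sponsor within 24 hours, whatever its cause. Then the rule changes: "Any SAEs experienced after the 30 days period should only be reported to Novartis if the investigator suspects a causal relationship to study treatment".

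**Early stoppers (section 5.7).** The rule covers "Subjects who discontinue study drug before completing the study, and those who prematurely withdraw from the study for any reason". These patients are due back 8 weeks (±1 week) after their final dose. On content, the section says: "at which time all of the assessments listed for the final visit will be performed". The assessment schedule (Table 5-1) marks adverse events at the final visit, Visit 15. For those who cannot or will not return, a floor applies: "At a minimum, they will be contacted for safety evaluations during the 30 days following the last dose of study drug". The last such contact falls on day 30.

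**Completers.** The last column of the schedule is Day 360. No later visit or call is specified for a patient who completes treatment.

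**Last dose.** The schedule marks drug administration on Day 360, and the PK sampling list in section 5.10.7 labels the Day 360 sample as pre-dose. The dose counts in section 3.1 lead to a last dose about a month earlier.

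**Patients who fail at month 1 (sections 3.1 and 5.5.5).** "Non-responder or deteriorating patients will be dropped from the study at the first month evaluations".

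**Other AE rules.** Section 5.6 has all AEs after consent entered on the CRF for treated patients and gives no end date. Section 6.1 records seriousness for each AE. Section 6.2.1 asks patients to report later events that they or their own physician think may be related, and sends any such SAE to the sponsor.

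**The concern.** Two parts of the plan use different end points for the same purpose. Section 5.7 treats 8 weeks after the last dose as a point worth assessing, adverse events included. Section 6.2.2 has by then stopped asking for SAEs regardless of cause. In the interval, whether the sponsor hears of a new SAE depends on a relatedness opinion. That opinion is formed in an open-label, single-arm study with no data monitoring committee and no adjudication committee (sections 7.4 and 7.5).

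The second problem is who gets the later look. The 8-week visit is written for patients who stop early. Completers have received the most drug and have the shortest specified follow-up after it.

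Safety is part of the primary objective (section 2), and section 8.5.2 rests the safety assessment mainly on AE frequency. With 10 patients, one more or one fewer patient with an SAE moves the proportion by 1/10, or 10 percentage points. There is no control arm against which unequal follow-up could be judged.

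**Working it through.** The 30-day window is a rule and not a calculated figure, so there is nothing to reproduce. The check is day arithmetic on the plan's own time points.

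**1. Gap for early stoppers.** Inputs: 30 days (6.2.2); 8 weeks ±1 week (5.7).
- Visit at 56 ± 7 = 49 to 63 days after the last dose.
- Gap: 49 − 30 = 19 days; 56 − 30 = 26 days; 63 − 30 = 33 days.

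**2. Last dose for completers.**
- Schedule: doses marked at Visit 1 and Visits 4 to 15 = 13 doses, the last on Day 360.
- Section 3.1, complete responders: 1 + 5 + 6 = 12 doses. Partial responders: 1 + 1 + 4 + 6 = 12 doses. With the first on Day 0 and steps of 30 days, the twelfth falls on Day 11 × 30 = 330.

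**3. Follow-up after the last dose.**

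| Patient | Last dose | All-cause SAE window closes | Last specified visit | Visit follow-up |
|---|---|---|---|---|
| Completer, by schedule and PK list | Day 360 | Day 390 | Day 360 | 0 days |
| Completer, by section 3.1 | Day 330 | Day 360 | Day 360 | 30 days |
| Dropped at month 1 | Day 0 | Day 30 | Day 49 to 63 | 49 to 63 days |

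In the first row the 30-day rule runs to Day 390 with no scheduled means of finding events. In the second row the window and the last visit coincide.

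**4. Sensitivity to visit timing.** Section 5.7 allows ±7 days on every post-baseline visit. If the Day 330 dose and the Day 360 visit both move, the 30 days become 30 ± 14 = 16 to 44, still below 49. Sections 3.2 and 5.5.4 speak of four-week spacing. Read literally, the twelfth dose would fall on Day 11 × 28 = 308, and Day 360 would be 52 days later. I use the 30-day steps because the schedule marks dosing at those visits.

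**5. Scale (assumed rates).** The documents give no SAE rate. Assume 0.1 to 1.0 per patient-year, with all 10 patients followed for the extra 26 days.
- Added time: 10 × 26 / 365.25 = 0.71 patient-years.
- Expected extra SAEs: 0.71 × 0.1 = 0.07 to 0.71 × 1.0 = 0.71.
- Chance of at least one, 1 − exp(−expected): 7% to 51%.

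**The case against.** The strongest reply is that section 6.2.2 governs what must be sent to the sponsor and does not end AE collection. A reader might infer that early stoppers have no all-cause SAE collection between day 30 and the 8-week visit. The documents do not support that. Section 5.6 sets no end date for CRF recording, the 8-week visit repeats the final-visit assessments, and section 6.1 records seriousness whatever the cause. This stands: for early stoppers who attend, what lapses is reporting to the sponsor of SAEs judged unrelated.

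Four other strong readings also fail.

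- *Late reporting rests on the investigator's opinion alone.* Section 6.2.1 adds the patient and the personal physician as triggers, and section 6.2.2 keeps follow-up of earlier SAEs open without limit. Neither route covers a new event that nobody thinks related.
- *Completers never have a visit after treatment.* That is so under the schedule and PK list. Under section 3.1, Day 360 falls 30 days after the last dose.
- *Patients dropped at month 1 miss the 8-week visit.* Section 5.7 covers premature withdrawal for any reason, which on its face includes them. The glossary says that no further assessments are planned at premature withdrawal, so the point needs confirming. Nor is rescue treatment tied to Day 30: section 5.5.6 foresees that decision as early as the first week.
- *The plan itself sets a 3-month risk period.* The live-vaccine rule in section 5.5.8 ("Live vaccinations within 3 months prior to the start of the trial, during the trial, and up to 3 months following the last dose") and the contraception rule in section 5.10.5 are precautions with different purposes and different starting points. Neither is a safety-observation period. The documents give no half-life, so they cannot show how much drug remains at day 30.

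It is also fair that the study is small, exploratory and descriptive, and that no statistical figure in the plan changes.

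**Conclusion.** The point holds in a limited form. All-cause SAE reporting to the sponsor closes 19 to 33 days (nominally 26) before the plan's own post-dose assessment of early stoppers. Completers, with 12 or 13 doses, have 0 to 30 nominal days of visit follow-up after the last dose, against 49 to 63 for a patient dropped after one dose. Loss of collection, as distinct from reporting, is a risk mainly for completers if a Day 360 dose is given, and for early stoppers who do not return.

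This rests on three assumptions: dosing takes place at the scheduled 30-day visits; section 5.7 is applied as written to month-1 withdrawals; and nothing outside these documents specifies a later contact for completers. The documents do not establish that 30 days is too short pharmacologically, or that a 3-month window is needed. The change is a cheap improvement to safety ascertainment, not the repair of an invalid analysis.

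**What to change.** 1. In section 6.2.2, run all-cause SAE reporting through the 8-week (±1 week) contact after the last dose, and state the same end for collection of all AEs.
2. In section 5.7, apply that contact, by visit or telephone, to completers as well, and state that it applies to patients dropped at month 1.
3. In section 5.7, move the minimum safety contact, now at 30 days, to the same end point.
4. Reconcile section 3.1 with the assessment schedule and section 5.10.7 on whether a dose is given on Day 360, and the monthly with the four-week wording on spacing. The follow-up calendar depends on the answer.

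Cost: a protocol amendment and one short contact per completer, at most about 10. The nominal last contact for a completer moves from Day 360 to Day 330 + 56 = 386 or Day 360 + 56 = 416. That is 26 or 56 days later, or about 1 to 2 months. No analysis method or sample size changes.

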### **6.3 Pregnancy reporting**

To ensure patient safety, each pregnancy occurring while the patient is on study treatment must be reported to Novartis within 24 hours of learning of its occurrence. The pregnancy should be followed up to determine outcome, including spontaneous or voluntary termination, details of the birth, and the presence or absence of any birth defects, congenital abnormalities, or maternal and/or newborn complications.

Pregnancy should be recorded on a Clinical Trial Pregnancy Form and reported by the investigator to the local Novartis Drug Safety and Epidemiology Department. Pregnancy follow-up should be recorded on the same form and should include an assessment of the possible relationship to the [investigational/study treatment] (*select*)

Any SAE experienced during pregnancy must be reported on the SAE Report Form.

### **6.4 Prospective suicidality assessment**

The Columbia-Suicide Severity Rating Scale (C-SSRS), a questionnaire that prospectively assesses Suicidal Ideation and Suicidal Behavior using a semi-structured interview to probe patient responses, has to be administered at each visit, including unscheduled ones.

If at any assessment after screening and/or baseline the score is 4 or above on the Suicidal Ideation item or any “yes” on the Suicidal Behavior item, the patient **must** be referred to a health care professional for further assessment and/or treatment. The decision on whether the study treatment should be discontinued is to be taken by the health care professional to whom the patient is referred to.

